This is a prospective, diagnostic accuracy study. For each lymph node sampled, we will alternate between the 19-g and the 21-g with each pass. Typically, an average of 5 passes is done in each lymph node (though number ranges from 3-12 based on physician judgment), for the study a minimum of 3 passes with each needle will be requested to provide adequate tissue for comparison. The choice of needle for the first pass will be randomized. More passes will be allowed with alternating needles based clinicians' judgment. Tissue obtained with the 19-g needles will be compared to tissue obtained with the 21-g needles with regards to diagnosis yield and adequacy for molecular testing.

b. Population:

i. Inclusion/Exclusion criteria

Inclusion:

- Age 18 years or older
- Able to provide informed consent
- Referred for EBUS TBNA sampling at Regions Hospital

Exclusion:

- On therapeutic warfarin, plavix or ticagrelor in the last 5 days

- INR >1.8, platelets <50K (evaluated at enrollment if patient has had them drawn as part of standard of care)
- ii. Sample size:

A total of 50 patients will be enrolled, with an average of 1.7 lymphnodes sampled in each patient. Patients will be a convenience sample of patients referred to have the EBUS-TBNA procedure at Regions Hospital during the study period.
- c. Data collection process
 - i. Process steps for identification of patients or records

All patients referred for EBUS TBNA sampling at Regions Hospital who meet the inclusion/exclusion criteria will be approached to be enrolled. These patients will be identified by one of the study investigators. Of note, the exclusion criteria for INR and platelets will have been drawn and evaluated as part of standard of care only, based on the concern for coagulopathy. These are not required to be drawn for study enrollment. All physicians who perform this procedure at Regions Hospital are listed as investigators on this study.
 - ii. Recruitment

Subjects will be identified based on referral for EBUS TBNA procedure at Regions Hospital by one of the study investigators. Because all physicians who perform the EBUS TBNA procedure at Regions are study investigators, one of the investigators will be aware of every patient referred to have this procedure. Upon becoming aware of a patient referred for this procedure, the study investigator will discuss the procedure with the patient.
 - iii. Consent

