After initial discussion of the procedure (standard of care), the investigator will describe the option to participate in the study as part of the procedure. The consent will be provided and reviewed with the patient/family, explaining the study verbally. The patient undergoing the procedure will provide consent for him- or herself and will be given sufficient time to privately review the consent form and discuss potential involvement in the study with any family members or LAR, as applicable. The investigator will again meet with the patient to address any questions and discuss enrollment. If appropriate, the investigator will obtain consent from the patient and begin the study procedures.
 - iv. Data Sources:

Data will be obtained before, during, and after the procedure. Demographic data will be obtained prior to the procedure via EMR. Number of passes with each size needle will be recorded in-person following each procedure. Diagnosis yield and adequacy for molecular testing will be obtained following the procedure, from the investigator performing the procedure and from pathology lab analysis as recorded in the EMR and communicated to the investigator per standard practice for this procedure. Complications will be assessed in-person during the procedure and following the procedure via review of the patient's EMR 24± hours after the procedure.
- d. Interventions, treatments

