The EBUS-TBNA procedure is done with both 19-g and 21-g needles as standard of care. The conduct of the procedure with both needle sizes in a systematic manner with concurrent data collection as described above is specific to the study. This procedure is conducted at Regions Hospital by the listed study investigators. The procedure typically takes between 20 and 90 minutes to complete, during which time the patient is under moderate sedation. During a standard procedure, the physician always performs at least four passes, sometimes more depending on the adequacy of the tissue being obtained. The average is 5.5 passes per lymph node. Participation in the study will likely result in an additional 1 to 2 total passes per patient. The randomization aspect of this study involves randomizing which needle size the physician starts with, with subsequent passes alternating between the two needle sizes. Initial needle size will be randomized using research randomizer. The randomization assignments for each study ID number will be kept in a document accessible by all investigators for use during enrollments. The investigators will not be blinded to the randomization assignment but the subjects will not be informed of which needle size they were assigned to start with.

e. Outcome/endpoint and other variable definitions, and instruments used

| Variable Name | Data Source | Purpose | Measurement Scale |
|--|---------------|-----------|-------------------|
| Ethnicity | EMR | Covariate | Categorical |
| Age and gender | EMR | Covariate | Categorical |
| BMI | EMR | Covariate | Categorical |
| Primary admission diagnosis | EMR | Covariate | Categorical |
| Secondary diagnoses | EMR | Covariate | Categorical |
| Passes with 21-g needle | In-person CRF | Covariate | Continuous |
| Passes with 19-g needle | In-person CRF | Covariate | Continuous |
| Total lymph nodes sampled | In-person CRF | Covariate | Continuous |
| Total sample yield 19-g | In-person CRF | Outcome | Continuous |
| Total sample yield 21-g | In-person CRF | Outcome | Continuous |
| Number of adequate samples by rapid onsite evaluation (ROSE) | In-person CRF | Outcome | Continuous |

| | | | |
|---|-------------------|-----------|-------------|
| Adequacy for molecular testing for lung cancer | In-person CRF | Outcome | Binary |
| Follow-up procedures required | EMR | Outcome | Categorical |
| Complications (hypotension, hypoxia, bleeding, other) | In-person CRF/EMR | Outcome | Categorical |

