This study will be conducted at Regions Hospital. Subjects will be identified by EBUS providers upon referral for the procedure. A letter of support from [name], Department head of Critical Care Medicine at Regions Hospital, is included with this application. We do not anticipate that the use of both needle sizes during the procedure will significantly affect the resources or personnel utilized during these procedures.

The Critical Care Research Center staff will be responsible for IRB correspondence and data management after collection. Study investigators are very involved with the study and have strong communication with the CCRC staff. The CCRC has conducted numerous studies in collaboration with the Regions Hospital Critical Care Medicine department.

This study fits with the organizational goals at Regions Hospital because it may help to improve patient satisfaction, decrease patient time under anesthesia, and decrease cost of diagnosis for subjects being evaluated with the EBUS TBNA procedure.

Investigator training: All investigators who will be performing the EBUS TBNA procedure are already trained in the conduct of the procedure and are already familiar with the use of both needle sizes. Prior to the start of the study data collection period, the investigators will attend a training meeting during which the specifics of the protocol will be reviewed and any questions discussed. A checklist will be made for use by the investigators during enrollments and investigators will be trained on this checklist and on the data collection instruments. Research staff will remain in close contact with the investigators and have a 24/7 research number where they can contact a research staff member. Investigators will notify CCRC research staff upon completion of enrollments and data collection for each patient. The research staff will collect all enrollment and data collection paperwork from the investigator. Data will be entered on a per-patient basis into an excel spreadsheet on the internal CCRC shared drive. Physical copies of patient study paperwork will be kept in a locked file cabinet in the CCRC, which is a limited access room that requires badge access with specific permission.

6. Risks and Benefits

Risks of EBUS-TBNA procedure

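### The starting-needle list is open to the investigators who enrol patients, so the only randomised factor (pass order) is not concealed; any resulting bias depends on an order effect the documents do not quantify

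*Combined protocol and SAP*

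**What the plan says.** Section 4.d confines randomisation to one element: "The randomization aspect of this study involves randomizing which needle size the physician starts with, with subsequent passes alternating between the two needle sizes". On how the sequence is made it says only: "Initial needle size will be randomized using research randomizer". No ratio or blocking is given. On who holds it: "The randomization assignments for each study ID number will be kept in a document accessible by all investigators for use during enrollments". It adds: "The investigators will not be blinded to the randomization assignment".

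The people with access also control entry to the study. Section 4.c.i says of eligible referrals: "These patients will be identified by one of the study investigators". Under 4.c.iii, once questions are answered and if appropriate, "the investigator will obtain consent from the patient and begin the study procedures". Section 4.d has the listed investigators performing the procedure. No section describes envelopes, an independent holder of the list, sequential issue of IDs, or disclosure only after consent.

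On sampling, 4.b.ii says: "Patients will be a convenience sample of patients referred to have the EBUS-TBNA procedure at Regions Hospital during the study period". Section 4.c.i intends every eligible referral to be approached.

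Both needles are used in each node (4.a) and the analysis is paired (4.f). The starting needle appears neither in the variable table in 4.e nor in the analysis plan in 4.f.

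**The concern.** Since every node receives both needles, randomising the first needle can serve only to balance order. That balance is protected when nobody deciding on enrolment can see the assignment. Here the deciding investigators have access to the list, and sections 2 and 3 show that they expect the 19-g needle to do better. Whether, when, or under which ID a patient is enrolled could become associated with the starting needle. If going first also carries an advantage, part of it could enter the needle comparison, and 4.f has no planned term that would show or adjust for this.

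Section 4.h lists unblinded providers and physician judgment as limitations. Concealment is a separate safeguard. An operator cannot be blinded to the needle in hand, but can be kept from knowing the assignment until the patient is enrolled.

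**Working it through.** **1. The plan's own yardstick.** Inputs from 4.g: 85 pairs (50 × 1.7), one-sided alpha 0.05, SD 10 points, power 80%. Taking the SD as that of the within-pair difference, the standard error is 10/√85 = 1.085. The detectable difference is (1.645 + 0.842) × 1.085 = 2.70 points, so the stated 2.7% reproduces. The hypothesised difference is 90 − 83 = 7 points.

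**2. What cancels.** Let d be the advantage, in yield points, of the needle that goes first. Within a node, the 19-g minus 21-g difference is the true difference plus d if 19-g starts, or minus d if 21-g starts. The node's underlying difficulty is in both yields and drops out.

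**3. Two routes to bias.**

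- Unequal starts, same d in all nodes: bias = d × (2s − 1), where s is the share of nodes starting with 19-g. With d = 2 and s = 0.6, this is 2 × 0.2 = 0.4 points. With s = 0.5 it is 0.
- Equal starts overall, but starting needle linked to difficulty: let half of nodes be hard, with a share p of them starting with 19-g and a share 1 − p of easy nodes doing so. Then bias = 0.5 × (2p − 1) × (d_hard − d_easy).

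The second route, in yield points:

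| d_hard − d_easy | p = 0.6 | p = 0.7 | p = 0.8 |
|---|---|---|---|
| 0 | 0 | 0 | 0 |
| 2 | 0.2 | 0.4 | 0.6 |
| 5 | 0.5 | 1.0 | 1.5 |
| 10 | 1.0 | 2.0 | 3.0 |

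Example: 0.5 × (2 × 0.7 − 1) × 5 = 1.0. The half-hard split, p and d are all assumptions; none is in the documents.

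**4. Simulation check.** True needle difference 0, hard nodes starting with 19-g 70% of the time and easy nodes 30%, and a 26-point difficulty gap. With an order effect of 2 points in both kinds of node, the bias was 0.00. With 6 points in hard nodes and 1 in easy nodes it was 1.00, as the formula gives.

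**5. Effect on the test.** At n = 85 and SD 10, a bias of b points gives a one-sided type I error of P(Z > 1.645 − b/1.085): 0.118 for b = 0.5, 0.235 for b = 1.0 and 0.397 for b = 1.5.

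**6. What a starting-needle term can do.** Averaging the mean difference in 19-g-first nodes with that in 21-g-first nodes removes the first route. It leaves the second. With p = 0.7, the average order effect is 0.7·d_hard + 0.3·d_easy in one group and 0.3·d_hard + 0.7·d_easy in the other. Half their difference is 0.2 × (d_hard − d_easy), the same bias as before. Only concealment addresses that route.

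**The case against.** The strongest case is that this is a within-node comparison with at least three passes per needle requested, so exposure to order is small. Much of it stands.

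- A reader might infer that more 19-g starts in hard nodes bias the result directly. They do not: difficulty cancels (steps 2 and 4).
- A reader might infer that investigators know every upcoming assignment and can pick IDs. The documents do not say when or how IDs are issued, and access for use during enrolment also fits a look-up after consent. What they do establish is that nothing prevents an earlier look.
- Assignments are by study ID, hence per patient, with 1.7 nodes on average. The list does not let an operator match individual nodes to a starting needle. If half of the 50 patients were hard cases, p = 0.8 would mean 20 of 25 of them starting with 19-g, which is extreme.
- Section 3 links needle size, not pass order, to trauma, blood and yield. It gives no direct support for an order effect.
- Large values of d are demanding. With alternation, the needles take passes 1, 3, 5 and 2, 4, 6. If yield is averaged over passes and only pass 1 benefits, d = 5 needs pass 1 to be 15 points better (5 × 3), and d = 10 needs 30.
- The criteria in 4.b.i are mostly objective, and 4.c.i has all eligible referrals approached. A convenience sample from one hospital is compatible with that, so the phrase is not evidence of selection. Approaching everyone limits the room for selection but does not conceal the list or fix the timing of enrolment.

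The acknowledgements in 4.h concern conduct of the procedure and do not answer the point about enrolment.

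**Conclusion.** The point holds in a limited form. The open list is a stated rule, and it leaves pass order unconcealed from the people who enrol. The documents do not show that selection will occur, that an order effect exists, or that the yield comparison is biased.

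Under the assumptions shown (half of nodes hard, 60-80% of these starting with 19-g, equal starts overall), the bias is 0 when the order effect is the same in hard and easy nodes. For a 5-point gap it is 0.5 to 1.5 points. That is 19% to 56% of the 2.7-point detectable difference (0.5/2.7 and 1.5/2.7), or 7% to 21% of the hypothesised 7 points. It would not account for a 7-point difference, but could matter for a result near the significance boundary. The change is worth making because it is cheap and protects the one factor the study randomises.

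**What to change.** In 4.d, replace the sentence on where the list is kept with wording to this effect:

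> The starting-needle list is held by CCRC research staff. Study IDs are issued in sequence. The starting needle is disclosed only after eligibility is confirmed and consent is signed, by sequentially numbered opaque envelope or by a call to the research number.

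The telephone route already exists: section 5 says that research staff "have a 24/7 research number where they can contact a research staff member".

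In 4.e, add the starting needle to the CRF, as assigned and as used. In 4.f, add it as a term in the yield model. In a model of the within-node difference it enters as a +1/−1 covariate. In a mixed model with one record per needle per node, the term should mark which needle went first, because a main effect of starting needle alone would not adjust the needle comparison. By step 6 of the working, this term complements concealment and does not replace it.

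Cost: 50 envelopes or one call per patient, a short step before each procedure, and a small added task for CCRC staff, whose stated duties in section 5 do not include holding allocations. Sample size, alpha and planned power are unchanged. Operator unblinding during the procedure remains.

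Rewording the convenience-sample phrase in 4.b.ii is optional: 4.c.i says that all eligible referrals are approached, not that they are enrolled consecutively.

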Study Title: Evaluation of 19-gauge vs 21-gauge EBUS TBNA in assessing thoracic lymphadenopathy

NCT # NCT03657849

Participant Contact Narrative: Evaluation of 19-gauge vs 21-gauge EBUS TBNA in assessing thoracic lymphadenopathy

1. Summary:

Endobronchial ultrasound-guided transbronchial needle aspirate (EBUS-TBNA) is a technique used to take samples of body tissue inside the chest without having to undergo an operation. During this procedure, a special telescope (called a bronchoscope) is inserted through the mouth into the airways. Ultrasound technology allows the doctor to see the structures just outside the airway. By being able to see the structures outside the airway, the doctor is able to safely pass a fine needle through the airway to take samples of abnormal tissue.

EBUS-TBNA is used to take samples of tissue from the mediastinum. The mediastinum is the part of the chest between the lungs, and contains the heart, gullet, windpipe and lymph nodes. This area of the body is usually difficult to access without open surgery, hence the use of EBUS-TBNA. EBUS-TBNA may be used to investigate enlarged lymph nodes. This may be due to tuberculosis, sarcoidosis or cancer.

Currently, smaller 21-gauge and larger 19-gauge needles are used during the EBUS-TBNA procedure at Regions Hospital. The purpose of this study is to find out which needle is better in finding the explanation for the enlarged lymph nodes, minimizing complications and any follow up procedures that may be necessary if we are unable to get enough tissue during the EBUS-TBNA procedure (surgical sampling, radiological sampling, and/or follow-up imaging).

2. Study Aims:

Using the larger 19-gauge needle instead of 21-gauge needle during EBUS TBNA will have higher yield without increasing complications

Primary outcome:

- 19-gauge needle yield vs 21-gauge needle yield (true positive + true negative)/total

Secondary outcome:

- Number of adequate samples by rapid onsite evaluation (ROSE)
- cytology assessment of sample size
- adequacy for molecular testing for lung cancer

H1: 19-gauge needle will have at least 7% higher absolute yield than 21-gauge needle (current yield for 21-g needle is 83%)

3. Background, Rationale, Significance:

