Endobronchial ultrasound (EBUS) transbronchial needle aspiration (TBNA) is regarded as the preferred initial sampling method in assessment of mediastinal and hilar lymph adenopathy [1]. There are several needle sizes available commercially (25-, 22-, 21-, or 19-gauge). The size of the needle may affect the

quantity of tissue obtained, degree of tissue trauma, and amount of aspirated blood; each of which can affect the diagnostic yield.

The 2016 CHEST guidelines [2], recommended the use of either 21- or 22-gauge needle during EBUS TBNA due to similar performance in the published literature but were unable to comment on other needle sizes due to lack of data. Since then few retrospective publications evaluated the recently available 19-gauge needle [3-8]. Biswas et al. repeated EBUS TBNA using 19-G needle in addition to 21-G needle for those patients with an initial negative 21-G EBUS TBNA but have high suspicion for sarcoidosis. The 19-G needle identified granulomas in all 11 patients compared to only 2 in the 21-G needle [4]. All these publications showed similar safety to smaller needles without increased bleeding risk.

One of the drawbacks of EBUS TBNA is the loss of the histological structure due to smaller needle size, leading to lower yield in diagnoses that require preserving the cell structure to make the diagnosis, such as lymphomas (yield 68%) and sarcoidosis (yield 78%) compared to malignancy (yield 90%) [2, 9].

When EBUS does not yield diagnosis, or doesn't provide adequate tissue for molecular testing, patients are usually subjected to further diagnostic testing including repeat imaging studies, and commonly proceeding with more invasive procedures or surgical operations to obtain tissue, which in addition to delaying the diagnosis, causes significant distress for the patients and increase the cost.

We believe that using 19-G needle during EBUS TBNA will improve the diagnostic yield overall and lead to more rapid diagnosis with fewer procedures for the patients which would improve patient's satisfaction and decrease overall cost. The use of a 19-G needle could also result ultimately in fewer total passes which would typically result in less time under sedation for the patient.

4. Approach:

a. Study design:

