| Total time sedated for procedure | In-person CRF/EMR | Covariate | Continuous |

f. Statistical analysis plan:

As each needle will be used for every lymph node evaluated, we will assume a paired data structure for analytic strategies. First, demographics and relevant patient factors in the study sample will be summarized using descriptive statistics. Bivariate comparisons (by needle gauge) will be conducted using McNemar tests, paired t-tests, or alternatives appropriate for paired data as dictated by the nature of each variable. If more flexibility is required (e.g., covariates for adjustment, specific correlation structure, random intercepts/slopes for patient clustering), we will specify linear mixed effects regression models to evaluate yield by needle gauge. For secondary aims (complications, etc.) we will employ descriptive analyses – no formal hypotheses will be tested.

g. Power analysis:

Assuming 85 paired samples (50 patients * 1.7 lymph nodes), a one-sided $\alpha=0.05$, and a standard deviation in yield of 10%, we expect 80% power to detect a mean difference of 2.7%. Given our anticipated yields of 83% (21g) and 90% (19g; 7% increase), we expect sufficient power to detect a statistically significant difference in average yield by needle gauge.

h. Strengths and Limitations:

Strengths of the study include:

- All physicians who perform the EBUS-TBNA procedure at Regions Hospital are investigators on this study, therefore we anticipate being able to approach all qualifying patients for enrollment.
- Both needle sizes are currently used as standard of care, based on physician discretion. Use of these needles in the study is not far from the current standard of care and could inform a more standardized methodology for needle size in the future

Limitations of the study include:

- Providers will not be blinded to needle gauge
- Difficult to attribute complications to a single needle gauge, given both will be administered
- As described above, procedural variation depends on physician judgment, which could bias results if judgment is differential with respect to needle gauge and/or yield

5. Setting/Environment/Organizational feasibility

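### Section 4.f leaves patient clustering of node-level needle differences to an optional model; one named patient-clustered test for yield would protect its level at little cost (minor)

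*Combined protocol and SAP*

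**What the plan says.** The primary outcome (section 2) is "19-gauge needle yield vs 21-gauge needle yield (true positive + true negative)/total". Section 4.f sets the unit of pairing: "As each needle will be used for every lymph node evaluated, we will assume a paired data structure for analytic strategies". Its default tests are these: "Bivariate comparisons (by needle gauge) will be conducted using McNemar tests, paired t-tests, or alternatives appropriate for paired data". Clustering enters one sentence later, as an example of when a linear mixed model might be used: "If more flexibility is required (e.g., covariates for adjustment, specific correlation structure, random intercepts/slopes for patient clustering". No criterion says when that model replaces the default, and no single test is named as primary for yield. Yield is the only outcome tested formally, since 4.f makes the secondary aims descriptive.

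Section 4.g counts nodes as the sample: "Assuming 85 paired samples (50 patients * 1.7 lymph nodes". It states a one-sided 5% level, an SD of 10%, and 80% power for a difference of 2.7%. Section 4.b gives 50 patients and an average of 1.7 nodes, but not how nodes are spread over patients.

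**The concern.** Nodes are nested in patients. A McNemar test or paired t on 85 node pairs takes its standard error from 85 independent differences. If two nodes of one patient tend to show the same needle difference, that standard error is too small, the one-sided test rejects too often and the interval is too narrow.

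The documents suggest two ways in which the difference could vary by patient.

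- **Diagnosis.** Section 3 describes "loss of the histological structure due to smaller needle size, leading to lower yield in diagnoses that require preserving the cell structure". The gain from the larger needle may therefore depend on diagnosis. That the nodes of one patient usually share a diagnosis is an assumption.
- **Starting needle.** Section 4.a says "The choice of needle for the first pass will be randomized", and 4.d adds "The randomization assignments for each study ID number will be kept in a document accessible by all investigators". If the start is set once per study ID, any advantage of going first acts in the same direction on all of a patient's nodes. Section 4.a does not rule out randomisation per node.

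**Working it through.** **1. The plan's own figure.** The inputs from 4.g are 85 pairs, one-sided 5%, SD 10 and 80% power.

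(1.645 + 0.842) × 10 / √85 = 2.70, which matches the stated 2.7%. With 50 pairs the same formula gives 24.87 / √50 = 3.52. So 4.g treats all 85 node pairs as independent.

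**2. What clustering does to the level.** The relevant ICC is that of the node-level differences (19-g minus 21-g). The documents do not give it, so a range is shown. The design effect is DEFF = 1 + (m* − 1) × ICC, with m* = Σm² / Σm. Three assumed layouts, each with 50 patients and 85 nodes:

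- 15 patients with 1 node and 35 with 2: m* = 155/85 = 1.82
- 25 with 1, 15 with 2, 10 with 3: m* = 175/85 = 2.06
- 30 with 1, 10 with 2, 5 with 3, 5 with 4: m* = 195/85 = 2.29

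The actual one-sided level of the plain test is 1 − Φ(1.645 / √DEFF). At ICC 0.1 the first layout gives DEFF 1.082, 1.645/√1.082 = 1.581 and a level of 5.7%. The third gives DEFF 1.129, 1.645/√1.129 = 1.548 and 6.1%.

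| ICC | DEFF | Level of plain test |
|---|---|---|
| 0 | 1.00 | 5.0% |
| 0.05 | 1.04-1.06 | 5.4-5.6% |
| 0.1 | 1.08-1.13 | 5.7-6.1% |
| 0.2 | 1.16-1.26 | 6.4-7.1% |
| 0.3 | 1.25-1.39 | 7.0-8.1% |

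Two-sided, the level is 6.0-6.5% at ICC 0.1 and 7.9-9.6% at ICC 0.3.

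**3. Which ICC the two routes could produce.** Take binary yield per node, with a proportion D of nodes discordant. Under a null with mean difference zero, the variance of a node difference is D. D is not given; 10% to 23.6% is assumed. The upper value is independent failure at the planned yields: 0.17 × 0.90 + 0.83 × 0.10 = 0.236.

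- First-needle advantage a, one start per patient: ICC = a²/D. For 10 points this is 0.01/0.236 = 0.04 to 0.01/0.10 = 0.10. For 15 points it is 0.0225/0.236 = 0.10 to 0.0225/0.15 = 0.15.
- Diagnosis, with assumed needle gaps of 22/12/0 points in a 10/30/60% mix. The gaps are the distances of the 68% and 78% yields in section 3 from the 90% for malignancy, borrowed as needle gaps. The mean gap is 0.1 × 0.22 + 0.3 × 0.12 = 0.058. The variance is 0.1 × 0.22² + 0.3 × 0.12² − 0.058² = 0.0058. The ICC is about 0.0058/0.236 = 0.025 to 0.0058/0.15 = 0.039.

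**4. Simulation of these nulls.** Each cell has 60,000 trials of 50 patients with about 1.7 nodes each. Diagnosis gaps are centred to a zero mean, and starts use simple 50/50 randomisation. One-sided level at nominal 5%:

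| Source of patient variation | Uncorrected McNemar or paired t | Exact McNemar |
|---|---|---|
| None | 4.9-5.3% | 2.1-3.2% |
| Diagnosis gaps | 5.0-5.7% | 2.9-3.4% |
| First needle, 5 points | 4.9-5.3% | 2.2-3.4% |
| First needle, 10 points | 5.2-6.0% | 2.5-3.6% |
| First needle, 15 points | 5.5-6.6% | 3.6-4.1% |
| Diagnosis plus first needle, 10 points | 5.4-6.0% | 3.3-3.8% |

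A patient-clustered robust test held 4.8-5.5% in all of these, and 4.7-5.5% in separate runs up to ICC 0.5. With uncentred diagnosis gaps, with or without a 10-point first-needle effect, 95% interval coverage was 93.7-94.7% for the plain paired t and 94.6-95.3% when clustered.

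**The case against.** The strongest reply is that the harm is close to nil. The plain tests run at 5.0-5.7% on the diagnosis route, which largely overlaps the clustered test's 4.8-5.5%. The highest first-needle figures need D equal to a, so that every discordant node favours the starting needle; at D of 0.20-0.236 the level was about 5.2-5.3% for 10 points and 5.6-5.7% for 15. Such effects exceed the 7-point needle effect in H1, and passes alternate. The diagnosis null has 19-g worse in the largest group and better elsewhere, which nothing in the documents suggests. With starts split exactly 25/25, a first-needle effect does not inflate the level (4.0-4.8%). All of this stands and is why the point is minor.

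Three stronger readings are tempting, and the documents support none of them.

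- A reader might infer that the plan overlooks clustering. It does not: 4.f names it, and its wording leaves room for other paired methods. What is missing is a commitment.
- A reader might infer that nested nodes inflate a paired test automatically. They do not: an effect shared by both needles cancels within the node. In simulations with only such an effect, asymptotic McNemar held 4.6-5.2%.
- A reader might infer that random intercepts correct nothing. Equality with the plain paired t appears when a node intercept is added, and 4.f does not name one. With a patient intercept alone the t-values differed (0.79 against 1.14; −0.48 against −0.71). What can be said is that a patient intercept alone does not model correlated needle differences, whereas a needle slope by patient does.

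**Conclusion.** The point holds as a minor one. For its only formally tested outcome, 4.f defaults to tests that treat node pairs from one patient as independent, and leaves clustering to an option without a trigger. The consequence depends on an ICC that the documents do not give: about 5% at ICC 0, 5-6% up to 0.1, and 7-8% at 0.3. The two routes in the documents, under the assumptions above, point to the lower part of that range, but the documents cannot settle it. An unconditional figure of 5-6% would therefore claim too much.

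The open choice of test also affects power. At a true 7-point difference with uncorrelated binary differences and discordance of 10, 15, 20 and 23.6%, uncorrected McNemar and the clustered test both have about 70, 52, 42 and 37% power. Exact McNemar has about 54, 41, 34 and 30%.

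The conclusion assumes that yield is analysed per node. Section 4.e lists a total yield per needle, and section 5 has data entered per patient. If yield is totalled per patient there is no clustering problem, but there are 50 pairs, not 85. The unit of yield and the 10% SD are separate issues and are not settled here.

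**What to change.** In 4.f, replace the open choice for yield with one primary analysis, for example:

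> Yield will be compared by the mean node-level paired difference (19-g minus 21-g). Its standard error will be clustered by patient with a small-sample correction and referred to a t distribution on the number of patients minus 1 degrees of freedom. The estimate will be reported with its confidence interval.

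With K patients, N nodes, node differences d and mean d̄, the squared standard error is K/(K − 1) × Σ over patients of (Σ over that patient's nodes of (d − d̄))² / N². For 50 patients the t has 49 degrees of freedom. If a mixed model is kept as a sensitivity analysis, specify a needle slope by patient.

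In 4.g, state that 2.7% assumes 85 independent pairs.

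The cost is a few lines of text and a data sheet that keeps yield by node and needle with the patient ID. In the diagnosis-gap scenarios the interval is about 1-4% wider. If differences are uncorrelated, almost nothing is lost: power at 7 points changes by at most 0.6 point (51.8% against 52.3% at 15% discordance). If starts are exactly 25/25 and a first-needle effect of 10-15 points exists, the clustered test is somewhat conservative (3.1-4.4%).
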